## 6.2 Efficacy

### 6.2.1 Primary Efficacy Endpoint

The primary efficacy **variable** is the change from baseline in 24h cough count after 12 weeks of intervention. Baseline is defined as the measurement at Visit 2. The raw 24h cough count will be standardized to an average hourly count, and then log-transformed for the analysis due to the expected range and distribution of the data. After applying a log-transformation, the data are expected to be normally distributed.

The data will be log-transformed first, before calculating any group means or changes from baseline, i.e. the observation of participant  $i$  at visit  $j$ ,  $x_{ij}$  will be transformed into  $y_{ij} = \log(x_{ij})$  with  $\log(\cdot)$  being the natural logarithm. All inferential statistics and modelling will

be based on the log-transformed observations  $y_{ij}$ . However, for easier interpretation of the magnitude of effects, the display of the results will focus on values on the original scale.

This results in display of geometric means for observations obtained at specific visits as

$$\begin{aligned} \exp(\bar{y}_j^{arith}) &= \exp\left(\frac{1}{n} \sum_{i=1}^n y_{ij}\right) \\ &= \exp\left(\frac{1}{n} \sum_{i=1}^n \log(x_{ij})\right) = \exp\left(\frac{1}{n} \log \prod_{i=1}^n x_{ij}\right) = \exp\left(\log \sqrt[n]{\prod_{i=1}^n x_{ij}}\right) = \bar{x}_j^{geo} \end{aligned}$$

where  $\bar{y}_j^{arith}$  and  $\bar{x}_j^{geo}$  denote arithmetic and geometric means, respectively.

Similarly, for the change from baseline, the arithmetic mean of the difference on the log scale translates into the ratio of geometric means on the original scale:

$$\begin{aligned} \exp(\bar{y}_{chg}^{arith}) &= \exp\left(\frac{1}{n} \sum_{i=1}^n (y_{ij} - y_{i,BL})\right) = \exp(\bar{y}_j^{arith} - \bar{y}_{BL}^{arith}) \\ &= \exp\left(\log(\bar{x}_j^{geo}) - \log(\bar{x}_{BL}^{geo})\right) = \exp\left(\log\left(\frac{\bar{x}_j^{geo}}{\bar{x}_{BL}^{geo}}\right)\right) = \frac{\bar{x}_j^{geo}}{\bar{x}_{BL}^{geo}} \end{aligned}$$

For ease of interpretation, in addition to the ratio of geometric means, the relative change (of geometric means) in % will be displayed as

$$\bar{x}_{rel\ chg} = \left(\frac{\bar{x}_j^{geo}}{\bar{x}_{BL}^{geo}} - 1\right) * 100\% = \frac{\bar{x}_j^{geo} - \bar{x}_{BL}^{geo}}{\bar{x}_{BL}^{geo}} * 100\%.$$

For cough counts per hour, any value smaller than 0.1 will be included into the analysis as 0.05 (in order to avoid taking the log of 0 if a response of 0 is recorded).

The **treatments** the primary analysis investigates are Eliapixant (25 mg, 75 mg, 150 mg BID), and placebo. The minimum required treatment duration is up to including Visit 3 for inclusion in the PPS.

#### Intercurrent events:

- a) Early discontinuation of study or study intervention for any reason: use data until discontinuation (while on treatment strategy). For handling the intercurrent event (ICE) of early discontinuation of the study and of the study intervention the while on treatment strategy will be applied. This strategy considers measurements of the endpoint up until the time of the intercurrent event. The last observation of the endpoint prior to the event will be used in the analysis. LOCF for all missing data due to early discontinuation will be applied.
- b) Non-compliance with study intervention: use data during compliant periods (while on treatment strategy) on a visit-by-visit approach:  
compliance will be calculated for the period between two consecutive visits. If the compliance is too low (i.e. below 80%), or too high (i.e. >120%, which is highly unlikely) the data collected during this period and the subsequent visit will not be used. Instead, the mean value of the observations between the adjacent compliant

visits (i.e. end point of the preceding compliant period and end point of the following compliant period) is taken. If there is no following period that can be used, LOCF will be applied. If there is no preceding compliant period, the mean value of the baseline value and the observation of the end of the first compliant period will be used.

- c) COVID-19 infection: use data prior to an active COVID-19 infection which is defined as the date of the first positive SARS-CoV-2 test or the date of the first positive serology IgG test or the start date of the AE confirming a COVID-19 infection (while on treatment), whichever is earliest. Symptoms of an acute COVID-19 infection are expected to have a major impact on the primary endpoint. Since long term effect of such an infection is unknown, only the data prior to the intercurrent event of an active COVID-19 infection will be used. LOCF imputation will be used in this case.

The **population** the primary estimand bases on is the population as described by the inclusion/exclusion criteria given in section 5 of the CSP and further by the PPS analysis population in section 5.1.

The **population-level summary** is the estimated geometric mean ratio (relative to baseline) of the primary efficacy variable by intervention group.

### 6.2.1.1 Primary Analysis

For the primary efficacy variable, it is planned to perform a test for a dose-response signal in the study population, under the assumption of a monotone dose-response relationship in the dose range considered. The MCP-Mod method [5] combining *multiple comparison procedures* principles with *modeling techniques* (MCP-Mod) will be used for the primary analysis of the primary efficacy variable. This method allows the flexibility of modeling for dose estimation, while preserving the robustness to model misspecification associated with MCP procedures. More specifically, it is planned to use a generalization of the original MCP-Mod method which allows to perform dose-response testing and modeling in conjunction with the response variable being described by a parametric model [6]. The key idea of this generalization is to decouple the dose-response model from the expected response so that the dose response can be characterized using a suitable parameter in the probability distribution of the response.

#### Assumptions

It is assumed that the primary efficacy variable, denoted as  $Y$ , is observed at the patient level for the 4 parallel groups corresponding to doses levels: (placebo =)  $d_1 < d_2 < \dots < d_K$ , where  $K = 4$ .

Furthermore, assume that the probability model for the patient responses  $Y$  includes parameters  $\mu_{d_1}, \dots, \mu_{d_K}$  for the changes from baseline in log (average hourly cough count) after 12 weeks of intervention capturing the dose-response effect for the doses  $d_1, d_2, \dots, d_K$ . This probability model may depend on other (nuisance) parameters and covariates.

Subsequently, it is assumed that the dose-response parameters  $\mu_{d_k}$ ,  $k = 1, \dots, K$  are related through a dose-response model  $\mu_d = f(d, \theta)$  where  $f(\cdot)$  is parameterized by a vector of parameters  $\theta$ . Let  $\hat{\mu}$  denote the vector of estimated dose-response parameters obtained from an appropriate estimation method for the assumed parametric model. The key assumption for the generalized MCP-Mod method is that  $\hat{\mu}$  has an approximate distribution  $N(\mu, S)$ , where  $S$  denotes the variance-covariance of  $\hat{\mu}$ . The estimates for  $\hat{\mu}$  and  $\hat{S}$  are obtained first, while the estimation of  $\theta$  is done in a separate second stage based on  $\hat{\mu}$  and  $\hat{S}$ .

The candidate set of models for  $f(\cdot)$  consists of four models, two Emax models with parameter  $ED_{50} = 30$  and  $ED_{50} = 50$  and two sigmoidal models with the parameters  $ED_{50} = 30$  and  $Hill = 3$ , and  $ED_{50} = 60$  and  $Hill = 5$ . All these candidate models assume a monotonically decreasing dose-response for the changes from baseline on the log scale. The parameters of the models are based on Phase 2a data and literature review. The dose-response candidate models are shown in Figure 6–1 and Table 6–1.

Figure 6–1: Candidate Set of Dose Response Curves

[figure not shown]

Table 6–1: Dose-Response Candidate Models

Model	Response as function of dose $d$
Emax1	$-0.19 - 0.42 * d / (30 + d)$
Emax2	$-0.19 - 0.47 * d / (50 + d)$
sigmoidal Emax1	$-0.19 - 0.35 * d^3 / (30^3 + d^3)$
sigmoidal Emax2	$-0.19 - 0.35 * d^5 / (60^5 + d^5)$

### Analysis

In a first step the mean parameter estimates from an ANCOVA model and the corresponding covariance matrix are obtained. After this step, these two parameters will then be used during the rest of the MCP-Mod procedure.

For the estimation of  $\hat{\mu}$  and  $\hat{\mathcal{S}}$  in the initial stage SAS will be used. All MCP-Mod steps will be performed using the R “DoseFinding” package (version 0.9-17 or higher) [7].

Step 1: Estimation of  $\boldsymbol{\mu}$  and  $\mathbf{S}$  from ANCOVA model with covariate adjustment

An ANCOVA model, following adjustment for baseline cough count and region via the inclusion of covariates  $z$ , will be used to estimate the expected dose response  $\mu_{d_k}$  in each dose group  $k$ .

For participant  $i$  the response is then defined by:

$$Y_{ki} = \beta_0 + z_{1ki}\beta_1 + z_{2ki}\beta_2 + \mu_{d_k} + \varepsilon_{ki}$$

where  $\varepsilon_{ki} \sim \mathcal{N}(0, \sigma^2)$ ,  $k = 1, \dots, K$  and  $i = 1, \dots, n_k$ .

Let  $\hat{\boldsymbol{\mu}}$  denote the vector of estimated dose-response and let  $\mathbf{S}$  denote the variance-covariance of  $\hat{\boldsymbol{\mu}}$ . The estimate of the covariance matrix  $\mathbf{S}$  will be denoted by  $\hat{\mathbf{S}}$ .

Step 2: Detection of dose-response signal

For detecting an overall trend, or a dose-response signal, each of the  $M=4$  dose-response shapes in the candidate set will be tested, using a single contrast test.

For each model  $m$  in the candidate set

the null hypothesis  $H_{0m}: (\mathbf{c}_m)' \boldsymbol{\mu} = 0$

will be tested against

the respective 1-sided alternative hypothesis,  $H_{1m}: (\mathbf{c}_m)' \boldsymbol{\mu} > 0$

where  $\mathbf{c}_m = (c_{m1}, \dots, c_{mK})'$  is the optimal contrast vector representing model  $m$ . The contrast coefficients for the  $m$ -th model are chosen such that they maximize the power for a single candidate model shape

$$\boldsymbol{\mu}_m^0 = (\mu_{m1}^0, \dots, \mu_{mK}^0)' = (f_m^0(d_1, \boldsymbol{\theta}_m^0), \dots, f_m^0(d_K, \boldsymbol{\theta}_m^0))',$$

where  $f^0$  is the standardized version of the dose-response model

$$f(d, \boldsymbol{\theta}) = \theta_0 + \theta_1 f^0(d, \boldsymbol{\theta}^0).$$

In this parameterization,  $\theta_0$  is a location parameter and  $\theta_1$  is a scale parameter such that only  $\boldsymbol{\theta}^0$  determines the shape of the model function. The optimal contrast coefficients  $\mathbf{c}_m$  depend only on the parameters in the standardized model function  $\boldsymbol{\theta}^0$ .

The optimum contrast coefficients and critical values for the four contrast tests on the dose-response shapes will be derived based on the guestimates for parameters  $\boldsymbol{\theta}^0$  of standardized versions of the models in the candidate set specified at the design stage, the actual sample size for each treatment group after study completion, and the covariance matrix  $\hat{\mathbf{S}}$  estimated from actual data [6].

Each dose-response model  $m$  will be tested using a single contrast test:

$$T_m = (\mathbf{c}_m)' \hat{\boldsymbol{\mu}} / [(\mathbf{c}_m)' \hat{\mathbf{S}} \mathbf{c}_m]_{m,m}^{1/2}$$

where  $[\mathbf{A}]_{m,m}$  denotes the  $m^{\text{th}}$  diagonal element of the matrix  $\mathbf{A}$ .

The final detection of a dose-response signal is based on the maximum contrast test statistic  $T_{max} = \max(T_1, \dots, T_4)$  and can be concluded if  $T_{max} > q_{1-\alpha}$ , where  $q_{1-\alpha}$  is the multiplicity adjusted critical value at level  $\alpha = 0.1$ . The MCP-Mod method takes multiplicity into account, and no further multiplicity adjustments are needed.

The selection of the best dose-estimation model will first be based on an assessment of the  $p$  value of the contrast tests. If no candidate model is statistically significant, the procedure stops indicating that a dose-response relationship cannot be established from the observed data. If there is one or more models with a significant adjusted  $p$  value, they will be retained and fitted as described in the next step.

Step 3: Modeling and estimation of target doses

The selected dose-response models (with a significant dose-response trend detected at the previous step) will be fitted to  $\hat{\mu}$  and  $\hat{S}$  to estimate the model parameters  $\theta$  using a generalized least squares (GLS) estimation criterion [6].

The evaluation of these models will be based on Akaike’s Information Criterion (AIC),  $p$  value and numerical stability.

In case more than one appropriate model has been identified, model averaging based on the individual model fits will be applied. The following weights for model  $m$  proposed by Buckland et. al. [8] will be used:

$$w_m = \frac{\exp(-AIC_m/2)}{\sum_{l=1}^L \exp(-AIC_l/2)}$$

To estimate the target dose(s) of interest the minimal effective dose (MED) will be determined:

$$MED = \operatorname{argmin}_{(d_1, d_4)} \{f(d, \theta) > f(d_1, \theta) + \Delta\}$$

where  $\Delta$  is a clinically relevant effect. The MED will be provided for the following change relative to placebo:

- -15%,  $\Delta = \log(0.85) = -0.163$
- -20%,  $\Delta = \log(0.8) = -0.223$
- -25%,  $\Delta = \log(0.75) = -0.288$
- -30%,  $\Delta = \log(0.7) = -0.357$
- -35%,  $\Delta = \log(0.65) = -0.431$

The final choice of the target dose will be based on the analyses of the primary, secondary and other efficacy variables, as well as safety considerations.

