9.4.2 Primary Endpoints

The primary efficacy endpoint is the change from baseline in 24h cough count after 12 weeks of intervention. Baseline is defined as the measurement at Visit 2. The raw 24h cough count will be standardized to an average hourly count, and then log-transformed for the analysis due to the expected range and distribution of the data. After applying a log-transformation, the data are expected to be normally distributed.

The primary analysis will be performed on participants in the PPS who have valid cough count measurements both at baseline and at least one post-baseline measurement. Supporting analyses will be performed on the FAS. Further sensitivity analyses will be specified in the SAP.

The MCP-Mod method combining MCP (multiple comparison procedures) principles with modeling techniques will be used for the primary statistical analysis. This method allows the flexibility of modeling for dose estimation, while preserving the robustness to model misspecification associated with MCP procedures.

3 active doses of BAY 1817080 will be used in this study: 25 mg, 75 mg, and 150 mg BID, with an additional placebo arm, corresponding to a 0 mg dose. The measurement of the primary efficacy endpoint at dose x will be a normally distributed variable μ_x , i.e., the change from baseline in log (average hourly cough count). For the dose-response relationship we assume

$$\mu_x = f(x, \theta) + \epsilon.$$

It is assumed that the change from baseline after 12 weeks of intervention is -0.19 under placebo and -0.54 at the maximum possible dose.

[figure not shown]
The candidate set of models for $f(x, \theta)$ consists of four models, two Emax models with parameter $ED_{50} = 30$ and $ED_{50} = 50$ and two sigmoidal models with the parameters $ED_{50} = 30$ and $Hill = 3$, and $ED_{50} = 60$ and $Hill = 5$. All these candidate models assume a monotonically decreasing dose-response. The parameters of the models are based on Phase 2a data and literature review. The dose-response candidate models are shown in [Table 9–1](#).

Table 9–1: Dose-Response Candidate Models

Model	Response as function of dose d
E _{max} 1	$-0.19 - 0.42 * d / (30 + d)$
E _{max} 2	$-0.19 - 0.47 * d / (50 + d)$
sigmoidal E _{max} 1	$-0.19 - 0.35 * d^3 / (30^3 + d^3)$
sigmoidal E _{max} 2	$-0.19 - 0.35 * d^5 / (60^5 + d^5)$

The corresponding dose-response relationships of the candidate models are shown in [Figure 9–1](#).

Figure 9–1: Candidate Set of Dose Response Curves

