## 2. Study Objectives

The objective of this study is to identify the optimal dose of P2X3 receptor antagonist Eliapixant in patients with RUCC and further assess efficacy and characterize safety and tolerability profile of Eliapixant .

The **primary** study objective is to

- assess the efficacy of P2X3 receptor antagonist Eliapixant as compared with placebo in terms of change in 24-hour cough count from baseline to week 12

The **secondary** study objectives are to

- further assess efficacy of Eliapixant
- further characterize safety and tolerability profile of Eliapixant

**Other** objectives are to

- further describe the efficacy profile of BAY 1817080 through the impact of intervention as patient reported outcomes
- to further evaluate the impact of the disease and associated comorbidities

A table that lists all primary, secondary and exploratory objectives with the corresponding endpoints can be found in section 3 of the CSP. Additional other objectives listed in the CSP refer to analyses that are outside the scope of this SAP, and thus are not described in this document.

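### The minimal effective dose rule has its inequality reversed, so as printed it returns essentially 0 mg for every target; nothing is defined for targets that are not reached

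*SAP*

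**What the plan says.** SAP section 2 gives the aim: "The objective of this study is to identify the optimal dose of P2X3 receptor antagonist Eliapixant in patients with RUCC". In SAP 6.2.1.1, Step 3, the target dose is estimated by the MED, the smallest dose in the open interval (d1, d4) satisfying "f(d, \theta) > f(d_1, \theta) + \Delta".

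The next line reads "The MED will be provided for the following change relative to placebo", followed by five targets from -15% to -35%. The first two are "\Delta = \log(0.85) = -0.163" and "\Delta = \log(0.8) = -0.223"; the others are -0.288, -0.357 and -0.431. All are negative.

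On direction, the Assumptions part of the same section states: "All these candidate models assume a monotonically decreasing dose-response for the changes from baseline on the log scale". Protocol 9.4.2 agrees: it assumes -0.19 on placebo and -0.54 at the maximum dose, so a more negative value is a better one. The Protocol contains no MED formula.

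The MED is one input among several: "The final choice of the target dose will be based on the analyses of the primary, secondary and other efficacy variables", together with safety.

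**The concern.** With a decreasing f and a negative Δ, a dose achieves the target reduction when f(d) lies at or below f(d1) + Δ. The printed rule asks for the opposite. It is met by doses whose effect is too small, beginning immediately above placebo, so it gives the same uninformative answer for all five targets.

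There is also a gap that does not depend on the sign. Step 2 says what happens if no candidate model is significant. Nothing says what is reported when there is a signal but no dose up to 150 mg reaches a given target. On the plan's own candidate curves, that is the situation for two of the five targets.

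If the text stays as it is, whoever programs the analysis must depart from the SAP to obtain a usable MED, and must choose a convention for unreached targets that was never pre-specified.

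**Working it through.** **Inputs.** The MED rule and the five Δ come from SAP 6.2.1.1, Step 3. The four candidate curves come from SAP Table 6-1 (the same as Protocol Table 9-1). Doses are 0, 25, 75 and 150 mg BID. Protocol 9.2 gives 50 per group, SD 0.8 and one-sided α = 0.10.

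**The plan's own figures.** Natural logs of 0.85, 0.80, 0.75, 0.70 and 0.65 are -0.1625, -0.2231, -0.2877, -0.3567 and -0.4308, so all five printed Δ are correct to three decimals. The maximum-contrast test has a critical value of 1.48 and power of 84.6%, 85.1%, 89.0% and 91.3% under the four curves, in line with the stated 85%. The design calculation is not in question.

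**The printed rule.** Rewrite it as f(d) - f(0) > Δ. As d falls to 0, the left side tends to 0, and 0 > Δ for every listed Δ. For any curve continuous at 0, the infimum is therefore 0 mg, and on an open interval no minimum is attained. On a grid of 0.0001 mg, the condition already holds at the first positive dose in 20 of 20 cases (5 targets × 4 curves). On a decreasing curve, the qualifying set runs from 0 up to the dose d* at which f(d*) - f(0) = Δ, and every dose in it falls short of the target.

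**Recoding does not help.** If benefit is coded as positive (g = -f, increasing) and Δ stays negative, g(d) > g(0) + Δ holds at every dose. Either the inequality must be reversed, or the signs of both f and Δ must change.

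**The rule with the inequality reversed.** Put x = -Δ and solve for d*:

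- Emax1: d* = 30x / (0.42 - x)
- Emax2: d* = 50x / (0.47 - x)
- Sigmoidal 1: d* = 30 [x / (0.35 - x)]^(1/3)
- Sigmoidal 2: d* = 60 [x / (0.35 - x)]^(1/5)

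For example, Emax1 at -15% gives 30 × 0.1625 / (0.42 - 0.1625) = 18.9 mg.

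| Target | Emax1 | Emax2 | Sigmoidal 1 | Sigmoidal 2 |
|---|---|---|---|---|
| -15% | 18.9 | 26.4 | 28.6 | 58.3 |
| -20% | 34.0 | 45.2 | 36.2 | 67.2 |
| -25% | 65.2 | 78.9 | 50.0 | 81.5 |
| -30% | not reached | not reached | not reached | not reached |
| -35% | not reached | not reached | not reached | not reached |

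Under the printed rule, these same values (mg BID) are the upper ends of the qualifying sets; for -30% and -35% the whole interval qualifies. The table only shows how the rule behaves on the design curves and recommends no dose.

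**Why two targets are missed.** The effects at 150 mg are:

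- Emax1: 0.42 × 150/180 = 0.3500
- Emax2: 0.47 × 150/200 = 0.3525
- Sigmoidal 1: 0.35 × 125/126 = 0.3472
- Sigmoidal 2: 0.35 × 97.66/98.66 = 0.3465

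These are reductions of 29.3% to 29.7%, below the 0.357 needed for -30% and the 0.431 needed for -35%.

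**Fitted curves.** The trial will use refitted, averaged curves. Simulation of 4,000 trials per candidate curve (50 per arm, SD 0.8) kept the model families with a significant contrast, refitted them and averaged by AIC weight. Given a signal, no dose up to 150 mg reached the target in 15-17% of trials for -25%, 35-39% for -30% and 56-63% for -35%. This rests on assumptions the SAP does not supply: no covariates, ED50 bounded to 0.15-225 mg, and Hill bounded to 0.5-10.

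**The case against.** The best reply is that this is a slip of notation which the text beside it resolves. Listing reductions relative to placebo leaves one sensible reading: the smallest dose that achieves at least that reduction. Step 2 also states its alternative in the generic upward form, so Step 3 looks like template notation into which benefit-signed Δ were inserted. The correct sign does not depend on the data, and the SAP can be amended before unblinding. The MED is calculated only after a signal, carries no decision threshold, and sits beside pairwise intervals, secondary endpoints and safety. All of this is fair, and it limits the weight of the point. It does not make the printed rule correct.

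It can also be said that the missing output is only a reporting convention, and that the non-attainment rates would be the same with a correct formula. That is so: they measure the size of the reporting gap, not harm from the reversed sign. They also move with the inputs; at an SD of 0.6, -30% is unreached in about 39-49% of trials. The miss at -30% on the design curves is narrow and comes partly from rounding, because Protocol 9.2 equates -0.35 with 30% whereas log(0.7) is -0.357.

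Finally, the sign is a single character in text converted from PDF, and the formula is not repeated elsewhere. A check of the original page is therefore warranted. The missing rule for unreached targets stands whatever that check shows.

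**Conclusion.** The point holds. As printed, the MED rule gives an infimum of 0 mg for all five targets on any fitted curve continuous at 0, and on a decreasing curve it picks out the doses that fail the target. Even with the direction corrected, the -30% and -35% targets have no MED up to 150 mg under any of the plan's four candidate curves, and no output is defined for that case.

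The conclusion about the sign needs only the stated direction of f, the negative Δ and the inequality as it appears in the text. The MED values assume the design-stage curves, and the non-attainment percentages rest on the simulation assumptions given with them.

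The error is confined to dose estimation: the contrast test, its error rate, the power and the sample size are untouched. Because the MED is the SAP's formula for the target dose in a dose-finding study, it should be corrected before unblinding.

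**What to change.** First check the printed sign against the original SAP page. Then define the MED as the smallest d in (d1, d4] with f(d, θ) ≤ f(d1, θ) + Δ. Using ≤ rather than a strict inequality means the minimum is attained on a continuous curve, and closing the interval at d4 lets 150 mg itself qualify. Add one sentence: when no dose up to d4 satisfies the condition for a given Δ, the MED for that target is reported as not reached within the studied range.

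The cost is one formula line and one reporting sentence in a SAP amendment, with no new data or analyses.
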